The Effectiveness and Mechanism Study
of Auricular Needling in Treating
Cancer Induced Anorexia

Research programme

2016. 05. 01

Background of the study

Anorexia nervosa is a common clinical symptom in tumor patients. The incidence of anorexia ranges from 6% to 74% depending on the type of tumor and clinical stage. It is common in patients with gastrointestinal tumors and advanced tumors, and the incidence of anorexia in advanced patients receiving palliative care ranges from 25% to 45%, and in severe cases, it is accompanied by malnutrition, or even malignant fluid state. In some studies, anorexia is found in up to 80% of patients with advanced stage, among which gastric cancer patients account for about 60%. Once anorexia occurs in tumor patients, it not only affects the implementation of the treatment plan, increases the difficulty of treatment, and affects the quality of survival of patients, but also can lead to malignant tumor patients die of malnutrition and depletion, which affects the survival time of the patients, and becomes the direct cause of death of tumor patients. Therefore, an in-depth understanding of the characteristics of anorexia nervosa, associated factors, assessment tools and interventions is an important therapeutic need faced by patients with advanced tumors, and a key direction for oncology research. How to optimize the selection of interventions against anorexia nervosa and to explore its mechanism of action are also scientific problems that we TCM oncologists need to solve in clinical practice. At present, the treatment of anorexia nervosa includes medication, nutritional therapy and psychotherapy, etc., with different efficacy and outstanding problems. Among them, megestrol acetate, as a kind of progestin with anabolic effect, has the functions of promoting appetite, increasing body weight, and improving the quality of patient's survival, and it is the only approved drug for the treatment of anorexia nervosa with cancer, but the toxic side effects caused by it, such as stimulation of tumor growth, venous thrombosis, and water and sodium retention, should not be ignored. Chinese herbal medicine has some research results in the treatment targeting the improvement of appetite, but it is not well accepted abroad. Clinical significance is insufficient. By combining the study of ancient literature with modern research, our department has taken a new approach to propose a new idea of clinical treatment, intervening auricular acupuncture in the treatment of cancerous anorexia nervosa. In the preliminary clinical pre-test, the initial effect is satisfactory, auricular acupuncture treatment can significantly improve the patient's appetite, showing its simple, convenient, inexpensive, tested characteristics, safe and reliable, but the technology needs further verification, standardization and improvement. However, this technique needs to be further validated, standardized and improved. Auricular acupuncture, which is highly accepted in the West, lacks high-quality evidence-based clinical efficacy and mechanism studies, which affects the influence of auricular acupuncture and warrants in-depth research.

This research proposal is in response to the National Natural Science Foundation of China's top-level project (Project No. 81573958; Title:

Auricular Acupuncture for Clinically Advanced Tumor Patients' Appetite Intervention and Mechanism Research).

Research Objectives

To objectively evaluate the clinical efficacy of auricular acupuncture in improving the appetite of tumor patients, to verify and improve its technique, to determine the therapeutic points and treatment course, and to provide a strong evidence-based medical basis for auricular acupuncture intervention in tumor therapy. We will validate and improve its technique, determine the therapeutic points and treatment course, and provide a strong evidence-based

medical basis for the intervention of auricular acupuncture in the treatment of tumors.

Research content

1 Type of study design

This study used a randomized, parallel-controlled research method. Based on the principle of voluntary participation, baseline information was included and collected, random seeds were generated by the SAS 9.2 statistical software random seed generator, and in a ratio of 1:1, it was proposed to randomly assign 60 subjects meeting the inclusion criteria to the ear acupuncture group and the control group. Each group of 30 cases, statistical expert design, after the preparation of the randomization scheme, the control and implementation of the allocation by those who are not directly involved in the grouping.

2 Sample size setting

This study was an exploratory study, considering 30 cases in each group, totaling 60 patients.

3 Study population

Sixty patients with anorexia nervosa of malignant tumors of stage III and IV who attended outpatient clinics or were hospitalized in the Department of Oncology of Xiyuan Hospital of China Academy of Traditional Chinese Medicine from May 1, 2016 to October 31, 2017.

3.1 Diagnostic criteria

3.1.1 Western medical diagnostic criteria

There is no uniform diagnostic standard for anorexia nervosa. Referring to the "Diagnostic and therapeutic pathway of anorexia nervosa" of the Professional Committee of Tumor Nutrition and Supportive Therapy of the Chinese Anti-cancer Association, based on the "Symptom-based assessment table", we shall evaluate whether anorexia nervosa occurs in the patients who are clearly diagnosed with tumors and the degree of its occurrence. The patient is asked to answer all the questions in the scale. After the patients answered all the questions in the scale, the scores were evaluated, and the final score ≤ 24 points could be recognized as anorexia.

3.1.2 Criteria for Chinese medicine

Refer to the "Guidelines for Clinical Research on New Chinese Medicines" (2002) for the diagnosis of "Plankton", spleen and stomach weakness, and the Guidelines for Clinical Research on New Chinese Medicines for the Treatment of Spleen-Qi Deficiency (Diagnosis of Chinese Medicine Symptoms), and the National Standard of the People's Republic of China - Chinese Medicine Clinical Diagnosis and Treatment - Terminology and Symptoms (GB/T 16751.2-), which were formulated by the National Committee of the People's Republic of China. 1997) are formulated.

3.1.2.1 Evidence of spleen (stomach) deficiency

Primary symptom: poor appetite and dullness, abdominal distension after eating or in the afternoon, abnormal stools (loose, hard and then loose, loose and hard).

Secondary symptoms: fatigue and laziness, tiredness and weakness, light mouth and no thirst, lingering abdominal pain, nausea and vomiting, gastrointestinal distension, intestinal tinnitus, yellowish color, swelling, weakness in defecation, emaciation, pale tongue, fat tongue or teeth marks, thin white moss, weak pulse.

If there are two main symptoms, or one main symptom plus two secondary symptoms, it can be diagnosed as Spleen (Stomach) Deficiency.

3.1.2.2 Non-Spleen (Stomach) Deficiency Symptoms

Any other syndrome that does not meet the diagnostic criteria of Spleen (Stomach) Deficiency.

4 Selection and Withdrawal of Subjects

4.1 Inclusion criteria:

- ① Patients with malignant tumors diagnosed pathologically/cytologically and with stage III or IV disease;
- ① Patients with malignant tumors diagnosed by pathology/cytology, with stage III or IV disease;
- ① Patients with malignant tumors diagnosed by pathology/cytology, with disease stage III and IV;
- ③ Age 18 ~ 80 years old, gender is not limited; ④ KPS score ≥ 60 points;
- ⑤ The estimated survival period is more than 3 months;
- ⑥ Patients who voluntarily accept the treatment of this trial, with informed consent and good compliance.

4.2 Exclusion Criteria

- ① Those who do not meet the inclusion criteria;
- ① Those who do not meet the inclusion criteria; ② Those who have abnormalities in blood routine, liver and kidney function indexes more than twice;
- Those with obvious eating disorders, gastrointestinal obstruction symptoms, heart disease and poor control of diabetes mellitus;
- ③ Those with obvious eating disorders, gastric obstruction symptoms, poor control of heart disease and diabetes mellitus;
- ⑤ Participating in other clinical studies;
- ⑤ Participants in other clinical studies; ⑥ Pregnant women, lactating women, psychiatric patients.

4.3 Withdrawal Criteria

Subjects may be withdrawn from this trial because of medical necessity in the opinion of the investigator, or because of the subject's own wishes. In all cases, the subject's results should be documented as much as possible, if possible.

Early withdrawal from the study may be considered by the patient and the investigator under the following circumstances:

4.3.1 Investigator-determined withdrawal

Withdrawal of a subject from a trial is a situation in which an enrolled subject becomes unfit to continue with the trial and the investigator decides that the case should be withdrawn from his or her trial.

- ① During the trial, the subject develops certain comorbidities, complications, or special physiological changes that make it inappropriate to continue the trial.
- (ii) The case was mistakenly included because it did not meet the inclusion criteria.
- (iii) During the trial, the subject's compliance is poor, affecting the validity and safety judgment.
- (iv) The use of drugs not within the prescribed range affects the validity and safety judgment.

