4.3.2 Self-withdrawal of subjects from the trial

According to the provisions of the informed consent, the subject has the right to withdraw from the trial in the middle of the trial, or the subject has not explicitly proposed to withdraw from the trial, but no longer accept the treatment and testing and lost visits, is also considered to be "withdrawing" (or "shedding"). As far as possible, the reasons for withdrawal should be

understood and documented. Regardless of the reason, a case record form should be kept for cases who drop out of the trial, and a full data set of efficacy and adverse events should be analyzed with the last test result carried forward as the final result.

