## Statistical analysis

### 1 Statistical analysis data set

#### ① Full Analysis Set (FAS)

is the ideal set of subjects that is as close as possible to the principle of intentional analysis (the primary analysis is to include all randomized subjects), and which is derived from the smallest and reasonably methodologically sound elimination of all randomized subjects. Estimates of missing values for the primary variables were carried forward (carry-forward) to the point where trial data were missing using the Last Observation Carry Forward (LOCF) method, with the number of subjects evaluating efficacy at endpoint remaining the same for each group as at the start of the trial. the FAS population was used for the analysis of the primary and secondary efficacy measures.

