### 2 Statistical analysis plan

Statistical analyses will be calculated using SAS 9.2 statistical analysis software.

The primary validity analysis dataset will be FAS, and PPS will also be analyzed.

All statistical tests will be two-sided, and a p-value of less than or equal to 0.05 will be considered a statistically

The differences tested were considered statistically significant.

Measures for each visit in the different treatment groups were described statistically as mean  $\pm$  standard deviation. Comparisons were made with the baseline values at the time of enrollment using the paired t-test. The paired t-test was used to compare pre- and post-treatment differences within groups. Changes before and after treatment in each group were compared using analysis of variance (ANOVA). The count data of each visit of different treatment groups were statistically described by frequency counts (constitutive ratio). Changes before and after treatment in each group were analyzed using the  $\chi^2$  test or nonparametric The  $\chi^2$  test or non-parametric test was used.

Shedding analysis: The  $\chi^2$  test will be used to compare the total shedding rate and the shedding due to adverse events in each group.

Balanced analysis of baseline values: ANOVA or  $\chi^2$  test will be used to compare demographic data and other baseline indicators to measure how well balanced the two groups are. measure how well the two groups are balanced.

Effectiveness analysis: PPS and FAS were used to analyze the primary and secondary indicators; since this study is a multicenter clinical trial, the impact of central effects on the efficacy indicators should be considered in the analysis. Since this study is a multicenter clinical trial, the influence of center effect on the efficacy indexes should be considered in the analysis.

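### Section 4.3.1 withdraws randomised subjects from the trial without saying that outcome assessments continue, so the full analysis set may rest on carried-forward values where outcomes could have been observed

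*Protocol*

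**What the plan says.** Protocol section 4.3.1 describes withdrawal from the trial, not only from treatment, on the investigator's decision. Besides medical complications it lists three reasons that concern conduct or eligibility:

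- (ii) mistaken inclusion: "The case was mistakenly included because it did not meet the inclusion criteria";
- (iii) poor compliance: "During the trial, the subject's compliance is poor, affecting the validity and safety judgment", with no threshold given;
- (iv) drugs outside a prescribed range, which the section does not define.

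On data after withdrawal, section 4.3 says only that "the subject's results should be documented as much as possible", and adds that this applies where possible. It sets no assessments for withdrawn subjects.

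On analysis, section 4.3.2 covers drop-outs whatever the reason and has them analysed "with the last test result carried forward as the final result". The SAP's definition of the full analysis set (FAS) also uses last observation carried forward (LOCF) for the primary variables and keeps the number evaluated at the endpoint equal to the number at the start. It says that "the primary analysis is to include all randomized subjects", while allowing a minimal, justified elimination of randomised subjects. The SAP separately defines a per-protocol set (PPS) by adherence, absence of banned drugs and a complete case record form.

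**The concern.** A subject who complies poorly, takes another drug or proves ineligible has not necessarily refused to be assessed. The visits at weeks 2, 4 and 8 are already scheduled (Protocol sections 6.5.2 and 6.5.3) and could still supply the main scales and weight. If withdrawal from the trial is read as the end of follow-up, those outcomes are lost without need. The subject is then counted in the FAS, but the final outcome is an earlier value and not an observation.

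The number lost may also differ by arm. Under section 5.2 the control is conventional care with no sham, so whoever judges withdrawal probably knows the allocation. Only the needling arm has a study procedure to comply with: embedded needles, self-pressing several times a day, and repeated sessions over 4 weeks. A compliance rule without a threshold could therefore fall more often on that arm. This is an inference from the design; the documents do not state it.

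At stake is the comparison of arms in the primary analysis set. With stage III and IV disease a later change in appetite is plausible, and a carried value misses it.

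**Working it through.** **The plan's own figure.** The protocol says "This study was an exploratory study, considering 30 cases in each group, totaling 60 patients". It gives no effect size, SD, power or drop-out rate, so 60 cannot be reproduced. For scale, with 30 per arm and two-sided 0.05 (SAP section 2):

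- standard error of a difference in means = √(2/30) = 0.258 SD;
- difference detectable with 80% power = (1.960 + 0.842) × 0.258 = 0.72 SD.

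**Error from carrying values forward.** The target is the difference that full follow-up of everyone randomised would show. In each arm let g be the mean change at the final visit in SD units, d the proportion withdrawn, and f the fraction of the change already reached at the last observation (0 = baseline carried, 0.5 = halfway). Assume that withdrawn subjects would have changed like the rest of their arm. Then

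- arm mean under LOCF = g × [(1 − d) + d × f];
- LOCF estimate = needling mean − control mean.

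All values of g, d and f below are assumptions.

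**Case 1: no true effect.** With the same g in both arms the estimate reduces to −g × (1 − f) × (d needling − d control). For g = −0.5, f = 0 and 20% v 0%, this is 0.5 × 1 × 0.20 = 0.10 SD. A positive value favours needling.

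| Common change g | Withdrawn, needling v control | f | Spurious difference | Simulated type I error |
|---|---|---|---|---|
| −0.5 SD | 10% v 10% | 0 | 0.00 | about 5% |
| −0.5 SD | 20% v 0% | 0.5 | 0.05 | not run |
| −0.5 SD | 20% v 0% | 0 | 0.10 | about 6.6% |
| −0.5 SD | 30% v 10% | 0 | 0.10 | about 6.6% |
| −1.0 SD | 20% v 0% | 0 | 0.20 | about 11% |
| +0.5 SD | 20% v 0% | 0 | −0.10 | not run |

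The error rates come from 20,000 simulated two-sample t-tests with 30 per arm. The simulation keeps the same spread for withdrawn subjects, so the rates are approximate. The 0.10 and 0.20 SD differences are 0.10/0.258 = 0.39 and 0.20/0.258 = 0.77 standard errors. Withdrawal of 20% of one arm is 6 of 30 subjects.

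**Case 2: a true effect.** Let needling change by 0.72 SD and control not at all, with 20% withdrawn from needling.

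- Baseline carried: 0.7234 × 0.80 = 0.58 SD, and power falls from 80% to 61%.
- Half the change carried: 0.7234 × 0.90 = 0.65 SD, and power is 71%.

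If poor compliers would have gained less than the others, the shortfall is smaller.

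**Direction.** A common decline with more withdrawal from needling favours needling. A common improvement with the same imbalance goes against it. A true benefit with control unchanged is diluted. Equal withdrawal with equal courses gives no bias.

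**The case against.** **Section 4.3 already asks for results to be documented.** No text forbids assessments after withdrawal, and withdrawal is permitted, not required. This stands in part: a reader might infer that the protocol orders follow-up to stop, and it does not. The gap is that nothing tells staff to continue, and a request to document what is possible is not a visit schedule.

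**The carry-forward sentence sits under self-withdrawal.** That is so, but its wording covers any reason for dropping out, and the SAP's LOCF rule is general. A reader might go further and infer that all three reasons certainly lead to a carried value. The documents do not settle that for mistaken inclusions: the elimination clause would allow their removal from the FAS, while the equal endpoint count points the other way. Neither route uses their later outcomes.

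**Arm dependence is not shown.** This stands. Needle compliance suggests more withdrawal from needling. It is tempting to add that controls would more often seek other appetite treatment, but the documents give no support for that; section 5.2 gives controls nutritional and symptomatic treatment and allows supportive therapy in both groups. No net imbalance can be claimed.

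**The plan has its own checks.** The SAP compares drop-out rates between groups by a chi-square test, and the PPS deals with adherence and banned drugs. With 30 per arm that test would detect only large imbalances, and neither step recovers an outcome that was not measured. The PPS does show that withdrawal from the trial is not needed to handle compliance.

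**The trial is exploratory and the shift is below one standard error.** This limits the weight of the point but does not remove it, since the remedy costs little.

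**Conclusion.** The point holds as a gap in the plan. The protocol does not say that assessments continue after withdrawal for reasons (ii), (iii) or (iv), and the analysis rules then put an earlier value, or possibly an exclusion, in place of outcomes that the FAS needs.

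The size cannot be taken from the documents, which give no withdrawal rate. Under the assumed 20% v 0% with baseline carried, no true effect and a common decline of 0.5 to 1.0 SD, the spurious difference is 0.10 to 0.20 SD against a standard error of about 0.26 SD. With equal withdrawal and equal courses it is zero.

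A reader might infer that the results will be tilted towards needling, or that LOCF will merely be conservative. The documents support neither, because the direction depends on withdrawal patterns and disease course that are not known in advance. The change is worth making because the loss is avoidable, not because a large bias has been shown.

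**What to change.** In Protocol section 4.3.1, state that withdrawal for reasons (ii), (iii) or (iv) does not end outcome collection. The main scales and weight continue at the scheduled week 2, 4 and 8 visits unless the patient withdraws consent or dies. Decisions about treatment stay with the investigator exactly as now.

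In the SAP, state that:

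- the FAS keeps these subjects, including mistaken inclusions, and uses their observed values;
- compliance, eligibility and outside drugs affect membership of the PPS only;
- values are imputed only where they are truly missing.

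The cost is a change of wording and a few assessments at visits that already exist. If 6 subjects were withdrawn before week 2, this would be at most 6 × 3 = 18 assessments. One small downside should be acknowledged: the FAS then estimates the effect of being assigned to needling, diluted by non-compliance. That fits the SAP's aim of staying close to all randomised subjects, and the PPS remains for the effect in compliers.

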4.3.2 Self-withdrawal of subjects from the trial

According to the provisions of the informed consent, the subject has the right to withdraw from the trial in the middle of the trial, or the subject has not explicitly proposed to withdraw from the trial, but no longer accept the treatment and testing and lost visits, is also considered to be "withdrawing" (or "shedding"). As far as possible, the reasons for withdrawal should be

understood and documented. Regardless of the reason, a case record form should be kept for cases who drop out of the trial, and a full data set of efficacy and adverse events should be analyzed with the last test result carried forward as the final result.

4.3.3 Discontinuation Criteria

- ① Occurrence of serious adverse events, complications and specific physiological changes that make continuation of the study inappropriate;
- ② Death;
- ③ Revocation of the experiment by the competent administrative department, etc.

4.3.4 Disengagement measures and criteria

The investigator should assess the health status and progress of the subject during the treatment period, and the subject can be discharged from the study at any time when the following conditions occur

When the following conditions occur, the subject can be withdrawn from the experiment at any time, and the investigator should provide symptomatic treatment.

- ① When the subject experiences intolerable skin irritation or localized pain;
- ② Decrease of more than 40 points per week in the Kahl score.
- ③ Weight loss of more than 30% per week.

5 Implementation of the program

5.1 Grouping of cases

In this study, 60 subjects who met the inclusion criteria were randomly divided into the ear acupuncture group and the control group according to the principle of randomized parallel control. Each group consists of 30 cases.

5.2 Treatment program

5.2.1 Ear acupuncture group

Ear acupuncture treatment + conventional nutritional support and symptomatic treatment (refer to "Diagnostic and therapeutic path of anorexia nervosa" of tumor nutrition and supportive therapy committee of China Anti-Cancer Association).

Commonly used main points: Shenmen, stomach, spleen, subcortex.

Auxiliary points: Sanjiao, sympathetic, liver, small intestine.

Methods: Embed an earring needle and fix it with adhesive tape, press each point for about 2 minutes each time, 2-3 times a day, the pressure depends on the tolerance of the individual, alternating between the two ears, 2-3 times a week, 4 weeks of treatment, observation until 8 weeks.

5.2.2 Control group: Conventional nutritional support and symptomatic treatment.

During the treatment period, both groups can use supportive therapy reciprocally, if there are treatment-related adverse events, they should be handled separately, and the causes, history, symptoms and treatment measures should be recorded in detail. During the treatment period, both groups of cases could adopt the international standard protocol (Version 3.2014 NCCN) with or without standard chemotherapy or or without standard chemotherapy or radiation therapy.

6 Observation Indicators

